3.3 Inclusion of Women and Minorities

Both men and women of all races and ethnic groups are eligible for this trial. BRAF mutant melanoma is more common in Caucasians and women, though metastatic melanoma is more common in men.

4. REGISTRATION PROCEDURES

4.1 General Guidelines for DF/HCC Institutions

Institutions will register eligible participants in the Clinical Trials Management System (CTMS) OnCore. Registrations must occur prior to the initiation of protocol therapy. Any participant not registered to the protocol before protocol therapy begins will be considered ineligible and registration will be denied.

An investigator will confirm eligibility criteria and a member of the study team will complete the protocol-specific eligibility checklist.

Following registration, participants may begin protocol therapy. Issues that would cause treatment delays should be discussed with the Overall Principal Investigator (PI). If a participant does not receive protocol therapy following registration, the participant's registration on the study must be canceled. Registration cancellations must be made in OnCore as soon as possible.

4.2 Registration Process for DF/HCC Institutions

DF/HCC Standard Operating Procedure for Human Subject Research Titled *Subject Protocol Registration* (SOP #: REGIST-101) must be followed.

5. TREATMENT PLAN

Treatment will be administered on an outpatient basis. A cycle of treatment will be 28 days in length. Patients are asked to maintain a medication diary for recording each dose of Dabrafenib, Trametinib and INCBO39110.

Reported adverse events and potential risks are described in Section 7. Appropriate dose modifications are described in Section 6. No investigational or commercial agents or therapies other than those described below may be administered with the intent to treat the patient's malignancy. The patient will be requested to maintain a medication diary of each dose of medication. The medication diary (Appendix C) and pill bottles will be returned to clinic staff at the end of each course. To document compliance, a pill count will be performed of all unused pills.

Dosing levels for the study are listed below in Table 5.1. Dose level 1 will be the first dose level. Dose escalation to the next dose level will occur when the preceding cohort reaches the end of Cycle 1. Patients who do not complete treatment in cycle 1 for reasons other than dabrafenib, trametinib or INCBO39110 toxicity will be replaced. Intra-patient dose escalation will be allowed when safe and feasible once the next higher dose level has been cleared. Additional, intermediate dose levels may be enrolled under the following conditions:

- 1) Toxicity is seen at a dose level where dose modification is necessary and the prior, lower dose level was treated without DLT or analysis of the PK data suggests that an intermediate dose would be appropriate;
- 2) An intermediate dose is conceivable based on the size of pills and nature of the toxicity at the higher dose;
- 3) IRB approval of an amendment to the protocol that clearly describes the rationale for and the logistics of the intermediate dose level.

Table 5.1 Dose Escalation Levels for Phase I Study

Dose Level	Dabrafenib [BID/PO]	Trametinib [QD/PO]	INCB039110 (mg QD)
-2	75 mg	1 mg	100 mg
-1	150 mg	2 mg	100 mg
1	150 mg	2 mg	200 mg
2	150 mg	2 mg	300 mg
3	150 mg	2 mg	400 mg

5.1 Pre-Treatment Criteria

5.1.1 Screening Visit: Patients must meet criteria at screening as outlined in Section 3.1.

- Of note, screening eligibility labs do not need to be repeated on cycle 1 day 1. If labs are drawn on Cycle 1, Day 1 will not be used to reconfirm eligibility. Eligibility is confirmed at screening; it is not required to be reassessed on Cycle 1, Day 1. Please see section 5.1.2 and the study calendar (Section 10) for information on laboratory studies and treatment parameters.

5.1.2 Hematologic Parameters for treatment:

Absolute Neutrophil Count

- Cycle 1, Day 1: $\geq 1,500/\mu\text{L}$
- Cycle 2 and Beyond, Day 1: Per Table in Section 6.2.1.1

White Blood Cell Count

- Cycle 1, Day 1: $\geq 3,000/\mu\text{L}$
- Cycle 2 and Beyond, Day 1: Per Table in Section 6.2.1.1

Hemoglobin

- Cycle 1, Day 1: $\geq 9\text{ g d/gl}$ (patients may be transfused to this level)
- Cycle 2 and Beyond, Day 1: Per Table in Section 6.2.1.1

Platelets

- Cycle 1, Day 1: $\geq 100,000/\mu\text{L}$
- Cycle 2 and Beyond, Day 1: Per Table in Section 6.2.1.1

5.1.3 Liver Function Parameters for treatment:

Transaminases (AST/ALT):

- Cycle 1, Day 1: $\leq 2.5 \times$ institutional upper limit of normal
- Cycle 2 and Beyond, Day 1: Per Table in Section 6.1.16

Bilirubin

- Cycle 1, Day 1: $< 1.5 \times$ institutional upper limit of normal
OR
 $> 1.5 \times$ institutional upper limit of normal allowed if direct bilirubin is within normal range
- Cycle 2 and Beyond, Day 1: Per Table in Section 6.1.16

5.1.4 Renal Function Parameters for treatment:

Creatinine:

- Cycle 1, Day 1: $\leq 1.5 \text{ mg/mL}$ OR creatinine clearance $\geq 50 \text{ mL/min}/1.73 \text{ m}^2$
- Cycle 2 and Beyond, Day 1: Per Table in Section 6.1.9

5.1.5 All Cycles, Day 1: Patients must have all the following:

- Adequate blood pressure control as detailed in Section 6.1.11.
- ECOG performance status of 0 or 1.
- No evidence of life-threatening medical problems.

5.2 Agent Administration

5.2.1 Trametinib

The effect of food on trametinib absorption is unknown. The current recommendation is to administer trametinib on an empty stomach, either 1 hour before or 2 hours after a meal; the recommendation to administer trametinib fasting may change based on emerging data. Missed doses of trametinib should not be made up if more than 6 hours have lapsed from the scheduled/planned dose time (i.e. no more than 30 hours from the previous dose). Vomited doses of trametinib should not be made up.

In the event that dabrafenib, INCB039110, or both agents need to be discontinued due to toxicity reasons, treatment with trametinib may continue at the discretion of the investigator until time of disease progression.

5.2.2 Dabrafenib

Patients should take dabrafenib at least 1 hour prior to or 2 hours after a meal due to a potential food effect on dabrafenib absorption. Doses should be taken every 12 hours. Missed doses of dabrafenib should not be made up if it is less than 6 hours until the next scheduled dose (section 8.1.2). Vomited doses of dabrafenib should not be made up.

In the event that trametinib, INCB039110, or both agents need to be discontinued due to toxicity reasons, treatment with dabrafenib may continue at the discretion of the investigator until time of disease progression.

5.2.3 INCB039110

INCB039110 is administered orally and provided in 100 mg tablets.

A positive food-effect was observed for all INCB039110 formulations studied at the 300 mg (3×100 mg) dose level. The SR3 formulation delivered a mean relative bioavailability of 48% and is likely to be associated with a moderate food-effect. The current recommendation is to administer INCB039110 on an empty stomach, either 1 hour before or 2 hours after a meal; the recommendation to administer INCB039110 fasting may change based on emerging data. Missed doses of INCB039110 should not be made up if more than 6 hours have lapsed from the scheduled/planned dose time (i.e. no more than 30 hours from the previous dose). Vomited doses of INCB039110 should not be made up.

In the event that trametinib, dabrafenib, or both agents need to be discontinued due to toxicity reasons, treatment with INCB039110 may continue at the discretion of the investigator until time of disease progression.

5.2.4 Concomitant Administration

Dabrafenib, INCB039910 and Trametinib may be taken together.

5.3 Definition of Dose Limiting Toxicity

Dose-limiting toxicity (DLT) is based on the CTEP Active Version 4 of the NCI Common Terminology Criteria for Adverse Events (CTCAE). DLT refers to INCB039110, Dabrafenib, or Trametinib treatment-related toxicities experienced during the first cycle of treatment between days 1-28. A DLT will be defined as follows:

- Any grade 4 toxicity
- Grade 3 non-hematologic toxicity
- Grade ≥ 3 neutropenia with fever $> 38.5^{\circ}\text{C}$
- Grade 3 thrombocytopenia with clinically significant bleeding
- Toxicity resulting in patients missing more than 20% of the doses

In general, all Grade 3, non-hematological toxicities related to INCB039110, Dabrafenib, or Trametinib regardless of duration are considered DLT. However, the following Grade 3 toxicities will not be considered a DLT.

- The appearance of cutaneous squamous cell carcinoma or keratoacanthoma will not be considered a dose limiting toxicity as these are commonly observed with dabrafenib.
- Grade 3 fatigue persistent for ≤ 7 days
- Grade 3 nausea, vomiting, or diarrhea persisting ≤ 72 hours with maximum supportive care
- Grade 3 electrolyte events if they are resolved with replacement within 24 hours
- Lymphopenia regardless of grade
- The following grade 3 laboratory abnormalities will not be considered dose limiting if they return to baseline in less than 7 days: elevated bilirubin, AST, ALT, cholesterol, amylase, lipase, creatinine and hypertriglyceridemia

Management and dose modifications associated with the above adverse events are outlined in Section 6.

Patients that have missed more than 20% of the doses for non-toxicity related reasons will not be considered evaluable for DLTs.

Dose escalation will proceed within each cohort according to the following scheme. Dose-limiting toxicity (DLT) is defined above.

Table 5.2. Dose escalation table

Number of Patients with DLT at a Given Dose Level	Dose Escalation Rule
0 out of 3	Proceed to the next dose level and enroll 3 patients
1 out of 3	Enroll and treat 3 additional patients at this dose level.
≥ 2 out of 3	Dose escalation will be stopped. The MTD will be one dose below this dose level. Three (3) additional patients will be entered at the next lower dose level if only 3 patients were treated previously at that dose.
1 out of 6	Proceed to the next dose level.

≥ 2 out of 6	Dose escalation will be stopped. The MTD will be one dose below this dose level. Three (3) additional patients will be entered at the next lower dose level if only 3 patients were treated previously at that dose.
If $\geq 2/3$ or $\geq 2/6$ patients at dose level 1 experience dose limiting toxicities, dose level -1 will be enrolled. If dose level -1 proves too toxic, the study will stop.	

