After repeat doses (Day 15), trametinib accumulated with a mean accumulation ratio of 6.6 at the RP2D of 2 mg QD. Between-subject variability in exposure ranged from 27-50% for C_{max} and 20-41% for AUC_{0-24} across all dosing regimens. The effective $t_{1/2}$ was approximately 4.5 days, and steady state was reached by approximately Day 15. Trametinib had a small peak:trough ratio of ~2 (Infante *et al.*, 2010). At 2 mg QD on Day 15, mean AUC_{0-24} was 376 ng•h/mL and C_{max} 23 ng/mL, and the mean trough concentrations ranged from 10.0 to 18.9 ng/mL. The long half-life and small peak:trough ratio of trametinib allowed constant target inhibition within a narrow range of exposure.

Drug-drug interactions:

Trametinib is metabolized predominantly via deacetylation (non-cytochrome P450 [CYP450]-mediated) with secondary oxidation or in combination with glucuronidation biotransformation pathways (Investigator's Brochure, 2012a). The deacetylation is likely mediated by hydrolytic esterases, such as carboxylesterases, or amidases. Based on *in vitro* studies, trametinib is not an inhibitor of CYP1A2, CYP2A6, CYP2B6, CYP2D6, and CYP3A4. Although trametinib was found to be an *in vitro* inhibitor of CYP2C8, CYP2C9, and 2C19; inducer of CYP3A4; and inhibitor of transporters (OATP1B1, OATP1B3,

P-glycoprotein [P-gp], and breast cancer resistance protein [BCRP]), its low efficacious dose, and low clinical systemic concentration (22.2 ng/mL or 0.04 mcM at 2 mg) relative to the *in vitro* inhibition/induction potency suggests an overall low potential for drug-drug interactions.

Pharmacodynamic effect and biomarkers:

The relationship between dose and tumor biomarkers such as pERK, Ki67, and p27, were evaluated in patients with BRAF or NRAS mutation-positive metastatic melanoma (Investigator's Brochure, 2012a). In general, increasing exposures and/or doses provided greater pharmacodynamic effects. The median change observed at a dose of 2 mg QD was 62% inhibition of pERK, 83% inhibition of Ki67, and a 175% increase in p27.

Antitumor Activity of Trametinib Monotherapy

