10. STUDY CALENDAR

Baseline evaluations are to be conducted within 2-week prior to start of protocol therapy with the exception of scans and x-rays. Scans and x-rays must be done \leq 4 weeks prior to the start of therapy.

Assessments must be performed prior to administration of any study agent. Study assessments and agents should be administered within \pm 3 days of the protocol-specified date, unless otherwise noted.

Procedure	Pre-Study	Cycle 1			Cycles 2+	End of Txt Visit	30 Day F-U Encounter ³	2-6 Month F-U
	Baseline ¹	Day 1 ^{2,b}	Day 8 ⁴	Day 15 ⁵	Day 1 ²			
Dabrafenib and Trametinib ^A		DT ----- DT						
INCB039110 ^B		I-----I						
Informed Consent ^a	X							
Demographic	X							
Medical History	X	X	X	X	X			
Concurrent Medication	X	X	X	X	X			
Serum pregnancy test (B-Hcg)	X ^c	X ^c						
Physical Examination	X	X		X	X	X		
Vital Signs (BP ^d , HR, body temperature)	X ^d	X ^d	X ^d	X ^d	X ^d	X ^d		
ECOG Performance Status	X	X	X	X	X	X		
Dermatology Examination ^e	X				X			X ^e
Height	X							
Weight	X	X			X	X		
Ophthalmology Examination ^f	X				X			
12 Lead EKG	X	X			X			
Hematology/Clinical Chemistry ^g	X	X	X	X	X ^h	X		
Coagulation ⁱ	X							
Tumor Measurements ^j	X ^j				X ^j			
PK Analysis ^k					X ^k			
Optional Tumor Biopsies ^l	X ^l		X ^l			X ^l		
Blood BRAF testing ^m		X		X	X	X		
Rash Prophylaxis ⁿ		X ⁿ		X ⁿ	X ⁿ			
AE assessment ^o	X	X	X	X	X	X	X	
Long term Follow up ^p								X ^p

Color Photography ^q	X ^q				X ^q			
Loperamide ^r	X ^r							

- A. Dabrafenib and Trametinib: doses as assigned; Dabrafenib BID and Trametinib QD.
- B. INCB039110: dosing as assigned per dose level.
- 1. All Pre-study assessments must be completed within 14 days prior to first dose, except for Scans that must be done within 28 days prior to first dose.
- 2. Assessment throughout the study is calendar based starting from first day of dosing (Day 1) in the first cycle of treatment. Dose interruptions should not alter the assessment schedule for any subsequent treatment cycle. Assessment for each visit can be done within 3 days of the projected visit date.
- 3. Follow up encounter, which can be carried out over the phone, should be 30 days from last dose of study drugs (\pm 3 days).
- 4. Medical History, Concurrent Medications, Vital Signs, ECOG Status, Hematology and Blood Chemistry panels will be completed prior to Day 8 treatment.

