- 5. Physical Exam, Medical History, Concurrent Medications, Vital Signs, ECOG Status, Hematology and Blood Chemistry panels will be completed prior to Day 15 treatment.
 - a. Informed Consent can be obtained within 28 days prior to the first dose.
 - b. If within 3 days of screening, this assessment does not need to be repeated on Day 1 of the first dose
 - c. Serum Pregnancy test (Woman of childbearing potential only) if done within 72 hours of first dose does not need to be repeated on Day 1 of the first dose.
 - d. In patients with blood pressure of systolic >140 mmHg and/or diastolic >90 mmHg, a second reading should be taken at least 1 minute later, with the two readings averaged to obtain a final BP measurement.
 - e. Dermatological Examination done at screening and then every 8 weeks (2 cycles). For patients enrolling in the expansion cohort who may have been on DT prior to enrolling and have had a recent skin exam, skin exams within 28 days of C1D1 will suffice for eligibility. Skin exams should continue every 2-3 months for 6 months after discontinuation of dabrafenib or initiation of another anti-neoplastic therapy.
 - f. Ophthalmological examination is done at screening, week 4, and annually. For patients enrolling in the expansion cohort who may have been on DT prior to enrolling and have had a recent ophthalmological exam that includes all requirements listed in Section 6.1.14, eye exams within 28 days of C1D1 will suffice for eligibility. Additional ophthalmic exams will be performed only as symptomatically warranted. For further details on requirements of exam see Section 6.1.14.
 - g. Clinical chemistries include sodium, potassium, carbon dioxide/bicarbonate, BUN creatinine, glucose, calcium, magnesium, phosphorus, AST, ALT, total Bilirubin, Alkaline phosphatase, total protein and albumin, LDH. Hematology includes CBC with differentials and platelets. Hematology samples will be collected before study treatment administration and at all applicable study visits
 - h. During Cycle 2, patients will have day 15 (+/- 3 days) clinical chemistries collected as outlined in footnote g above. After cycle 2, clinical chemistries are collected on Day 15 at the investigator's discretion.
 - i. Includes PT, PT-INR, PTT, repeated as indicated. These chemistries may be collected at a remote facility and the results can be faxed to the research team.

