13. STATISTICAL CONSIDERATIONS

13.1 Study Design/Endpoints

This is a phase I trial of the combination of dabrafenib, trametinib, and INCB039110 in patients with BRAF-mutant advanced solid tumors. The primary objective of the study is to determine the maximum tolerated dose (MTD) of the combination; secondary objectives will provide preliminary estimates of efficacy and toxicity. The escalation and stopping rules imply that the incidence rate for DLT will be less than 33% at the MTD. Following the identification of the MTD, up to an additional 20 patients will be enrolled in a dose expansion cohort at the MTD.

Toxicities and lab values will be graded according to the NCI Common Toxicity Criteria for Adverse Events (v4.0). Dose-limiting toxicities will be scored and will be defined as in Section 5.2.

Dose escalation will use a standard “3+3” approach, beginning in dose level 1, with dosing and rules for escalation and de-escalation described in the tables below. Tolerability assessments will be based on cycle 1 alone. The MTD is defined as the highest dose level at which 0 or 1 of six patients has experienced a DLT. If an excessive number of toxicities occur at the initial dose level 1, the dose will be reduced to the fall-back dose of -1. If dose level -1 has excessive toxicity, the study will stop.

Number of Patients with DLT at a Given Dose Level	Dose Escalation Rule
0 out of 3	Proceed to the next dose level and enroll 3 patients
1 out of 3	Enroll and treat 3 additional patients at this dose level
≥ 2 out of 3	Dose escalation will be stopped. The MTD will be one dose below this dose level. Three (3) additional patients will be entered at the next lower dose level if only 3 patients were treated previously at that dose.
1 out of 6	Proceed to the next dose level.
≥ 2 out of 6	Dose escalation will be stopped. The MTD will be one dose below this dose level. Three (3) additional patients will be entered at the next lower dose level if only 3 patients were treated previously at that dose.
If $\geq 2/3$ or $\geq 2/6$ patients at dose level 1 experience dose limiting toxicities, dose level -1 will be enrolled. If dose level -1 proves too toxic, the study will stop.	Dose escalation will be stopped. The MTD will be one dose below this dose level. Three (3) additional patients will be entered at the next lower dose level if only 3 patients were treated previously at that dose.

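### Asymptomatic laboratory and ECG toxicity from late cycle 1 can first be seen after the Day 28 DLT window closes, and escalation need not wait for those results

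*Combined protocol and SAP*

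**What the plan says.** - **DLT window.** Section 5.3 limits DLT to treatment-related toxicity "experienced during the first cycle of treatment between days 1-28". Section 13.1 adds: "Tolerability assessments will be based on cycle 1 alone".
- **Cycle length.** Section 5: "A cycle of treatment will be 28 days in length". Cycle 2 Day 1 is therefore nominally Day 29.
- **Escalation trigger.** Section 5: "Dose escalation to the next dose level will occur when the preceding cohort reaches the end of Cycle 1". Neither Section 5 nor Table 5.2 mentions Cycle 2 Day 1 results.
- **Laboratory tests.** The Study Calendar (Section 10) has cycle 1 columns for Days 1, 8 and 15 only. Footnote 5 covers the last of these: "Hematology and Blood Chemistry panels will be completed prior to Day 15 treatment". The next scheduled panel is at Cycle 2 Day 1.
- **ECG.** It is marked at baseline, Cycle 1 Day 1 and Day 1 of later cycles, with no mark at Day 8 or Day 15. The calendar requires assessments before dosing, so the Cycle 1 Day 1 tracing is pre-treatment.
- **Visit window.** Footnote 2: "Assessment for each visit can be done within 3 days of the projected visit date".
- **What counts.** Under Section 5.3, any Grade 4 toxicity except lymphopenia is a DLT, and so is most Grade 3 non-hematologic toxicity. Grade 3 neutropenia counts only with fever, and Grade 3 thrombocytopenia only with significant bleeding. Listed Grade 3 chemistries do not count if they recover to baseline inside a week, nor do Grade 3 electrolyte events corrected within a day.

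**The concern.** DLT drives every escalation decision, the MTD, and so the dose given to up to 20 expansion patients. Toxicity that a patient feels can be dated by history, because adverse events are assessed from Day 1 onward. Toxicity that shows only on a blood test or ECG has no date until it is tested. For such an event arising after the Day 15 visit, the first scheduled test is nominally one day after the window shuts. The plan does not say whether a pre-dose Cycle 2 Day 1 finding belongs to cycle 1, and the Section 13.1 sentence on cycle 1 points against counting it.

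Two consequences follow. Scoring can turn on the appointment date: the same silent abnormality falls inside the window if drawn on Day 28 and outside it if drawn on Day 29. The next cohort can also open before the result exists. Any loss of events works in one direction only, toward fewer scored DLTs and a higher declared MTD.

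Laboratory toxicity is not peripheral here. Section 6.2.1 names falling neutrophils, hemoglobin and platelets as the only consistent effects of INCB039110. The safety table in Section 2.3.2.4 gives Grade 3-4 rates on the 150/2 doublet of 13% for neutropenia, 11% for hyponatremia, 5% for AST, 4% for ALT and 5% for creatinine. Those rates are not limited to cycle 1, and many such events would not be DLTs.

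**Working it through.** **1. Day arithmetic.** Cycle 2 Day 1 = 28 + 1 = Day 29. With the visit window it is 29 - 3 = Day 26 to 29 + 3 = Day 32. The Day 15 visit can fall on Days 12 to 18. On nominal dates, Days 16 to 28 have no scheduled panel: 28 - 15 = 13 days, and 13/28 = 46% of the window. On nominal dates no on-treatment ECG falls within Days 1 to 28.

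**2. Reproducing the plan's figure.** With true DLT rate p and q = 1 - p, the 3+3 rule escalates on 0 of 3, or on 1 of 3 followed by 0 of 3:

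P(escalate) = q³ + 3pq² × q³

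| True rate | 0.10 | 0.20 | 0.30 | 0.40 | 0.50 | 0.60 |
|---|---|---|---|---|---|---|
| Section 13.1 | 0.91 | 0.71 | 0.49 | 0.31 | 0.17 | 0.08 |
| Computed | 0.906 | 0.709 | 0.494 | 0.309 | 0.172 | 0.082 |

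All six values match. The table takes every DLT as scored.

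**3. Effect if some are not scored.** The share f of DLTs found only by tests is not in the documents; I assume 10% to 50%. I also assume that onset is uniform over 28 days and that every test-only event arising on Days 16 to 28 is missed. The scored rate is then

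p_obs = p × (1 - f × 13/28)

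The overall share missed is f × 13/28: 4.6% at f = 10%, 11.6% at 25% and 23.2% at 50%.

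| f | True 33%: p_obs | P(escalate) | True 40%: p_obs | P(escalate) |
|---|---|---|---|---|
| 0 | 0.330 | 0.43 | 0.400 | 0.31 |
| 10% | 0.315 | 0.46 | 0.381 | 0.34 |
| 25% | 0.292 | 0.51 | 0.354 | 0.39 |
| 50% | 0.253 | 0.59 | 0.307 | 0.48 |

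Worked line for 33% and f = 50%: p_obs = 0.33 × (1 - 0.232) = 0.253 and q = 0.747, so P = 0.416 + 0.424 × 0.416 = 0.59.

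The 33% row matters because Section 13.1 says the rules imply a DLT rate below 33% at the MTD.

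**The case against.** **Day 29 is only nominal.** A reader might infer that the end-of-cycle tests always fall outside the window. They do not: footnote 2 allows Days 26 to 28, and the Day 15 panel may be drawn as late as Day 18. This stands. The exclusion depends on the visit date and is not certain.

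**Section 5.3 uses onset language.** It speaks of toxicity experienced in the window, and nothing says that an event is dated at detection. A pre-dose sample on Day 29 reflects cycle 1 exposure, so an investigator could assign it to cycle 1. Exclusions that turn on recovery within a week also imply use of later information. This is fair, but it leaves the choice to the individual investigator, and the trigger in Section 5 still does not wait.

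**The eye exam.** A reader might add it to the list of late tests, since it is marked in the Cycles 2+ column. The documents do not support that. Table 6-11 describes asymptomatic RPED as Grade 1, which is not a DLT, and Grades 2-3 as symptomatic. Footnote f says: "Ophthalmological examination is done at screening, week 4, and annually". Week 4 literally ends on Day 28.

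**Few event types are affected.** Uncomplicated Grade 3 neutropenia and thrombocytopenia, all lymphopenia and short-lived listed Grade 3 chemistries are excluded anyway. This stands and narrows the point.

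**Exposure.** It is tempting to say that the gap coincides with first full exposure, since for trametinib "steady state was reached by approximately Day 15". That argument is weak. From dose level 1 to 3 only INCB039110 changes, and its sustained-release half-lives of 6.5 to 13 hours (Section 2.2.3) suggest steady state within days. Patients may also enter already on dabrafenib and trametinib (Section 3.2.1).

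**Other safeguards.** Pyrexia, seen in 71% on the 150/2 doublet, triggers a laboratory work-up under Table 6-2. The DSMC may receive DLT data, PK and safety are reviewed before expansion, and the expansion cohort adds toxicity data. The triggered tests make the assumption that every event is missed a pessimistic one. The reviews do not define how a Cycle 2 Day 1 finding is scored.

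**Conclusion.** The concern holds in a limited form. As written, the plan can leave asymptomatic Grade 4 laboratory events, persisting Grade 3 chemistries and severe QTc findings that arise after the Day 15 visit out of the primary endpoint, depending on the date of the Cycle 2 Day 1 visit. It also allows escalation before those results exist. That gap is in the wording of the window and the trigger, and it can be read directly from Sections 5, 5.3, 10 and 13.1.

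The size is not known. The increases to 0.46-0.59 (from 0.43, at a true rate of 33%) and to 0.34-0.48 (from 0.31, at 40%) rest on an unsourced 10% to 50% share, uniform onset, and no detection of any Day 16-28 test-only event before the window closes. They show direction and sensitivity. A reader should not take them as an estimate of bias in this trial, nor conclude that the protocol's escalation table is wrong: it is correct when every DLT is scored.

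**What to change.** 1. In Sections 5.3 and 13.1, define the DLT period as Cycle 1 Day 1 through the later of Day 28 and the Cycle 2 Day 1 pre-dose laboratory tests and ECG. State that treatment-related abnormalities first found at those assessments count as cycle 1 DLTs if they meet the Section 5.3 criteria. The later-of wording keeps an early visit from closing the window before Day 28.
2. In Section 5 and Table 5.2, state that the escalation decision is made only when these results are available for every evaluable patient in the cohort.
3. Separately, reconcile the eye exam timing in footnote f with its mark in the Cycles 2+ column of the Study Calendar. This is a consistency point and does not bear on the DLT argument.

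The cost is small. All the tests are already scheduled, so only wording changes. Cohort opening may wait a few days, and observed DLT rates may be slightly higher. The end of the DLT period would still vary between Day 28 and Day 32 with the visit date, but an end-of-cycle finding would count whichever of those days it was drawn on.

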
Criteria for discontinuing study drug: When any of the liver stopping criteria below is met, discontinue trametinib and dabrafenib
 
 1. ALT \geq3xULN and Total bilirubin \geq2x ULN or $>35\%$ direct bilirubin^{1,2} 2. ALT \geq 3xULN and INR >1.5, if INR measured and if subject is not on anticoagulation² 3. ALT \geq5x ULN 4. ALT \geq3x ULN persists for ≥ 4 weeks 5. ALT \geq3x ULN and cannot be monitored weekly for 4 weeks 6. ALT \geq3x ULN associated with symptoms³ (new or worsening) believed to be related to liver injury or hypersensitivity 	
 • Immediately discontinue study treatment. • Do not restart/rechallenge • Perform liver event ASSESSMENT AND WORKUP (see below). • Monitor the subject until liver chemistries resolve, stabilize, or return to baseline (see MONITORING below). If applicable, provide details on required follow up assessments (e.g., follow up for overall survival or disease recurrence or progression). 
MONITORING: In patients stopping for criteria 1-2 (with abnormal TB and INR, indicating potentially more significant liver toxicities):
 
 • Repeat ALT, AST, ALK, and total bilirubin) and perform liver assessment and workup within 24 hours. • Monitor subjects twice weekly until LFT return to normal/baseline or stabilize. • A specialist or hepatology consultation is recommended. 
In patients stopping for criteria 2-6:
 
 • Repeat LFT and perform liver event follow up assessments within 24-72 hours • Monitor subjects weekly until LFTs return to normal/baseline or stabilize. 
ASSESSMENT and WORKUP:
 
 • Viral hepatitis serology.⁴ • If possible, obtain blood sample for PK analysis.⁵ • Serum CPK and LDH. • Fractionate bilirubin, if total bilirubin \geq2x ULN.

Event	Treatment modifications and assessment/monitoring

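### A brief Grade 3 ALT rise that permanently stops dabrafenib and trametinib is a DLT through about Day 23 of Cycle 1 but a non-DLT from about Day 24 (minor)

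*Combined protocol and SAP*

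**What the plan says.** Section 5.3 counts treatment-related toxicity on Days 1-28. It lists five alternative DLT criteria, among them any Grade 3 non-hematologic toxicity and, with no grade attached, "Toxicity resulting in patients missing more than 20% of the doses". It then restates the Grade 3 rule and lists exceptions to it, including Grade 3 "laboratory abnormalities will not be considered dose limiting if they return to baseline in less than 7 days: elevated bilirubin, AST, ALT" and several others. Management is referred to Section 6. Permanent discontinuation is not itself a DLT criterion.

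Section 6.1.16, Table 6-14, says: "When any of the liver stopping criteria below is met, discontinue trametinib and dabrafenib". Criterion 3 is ALT at or above 5x ULN. The action includes "Do not restart/rechallenge", with no allowance for quick recovery. Section 6.2 lets INCB039110 continue at the investigator's discretion.

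Section 13.1 judges tolerability on Cycle 1 only. Sections 5 and 13.1 do not replace a patient who stops for toxicity, so the patient must be scored one way or the other.

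**The concern.** The same liver event with the same consequence is scored differently according to the day on which it is acted on. A patient stopped on Day 8 or Day 15 misses well over 20% of both drugs and is a DLT. A patient stopped in the last days of Cycle 1 has too few doses left to miss 20%. The exemption then decides the case, and the patient counts as having tolerated a dose of which two of the three components are permanently withdrawn.

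The MTD is the primary objective and cohorts are of three or six. One reclassified patient turns 0/3 into 1/3, so three more are enrolled, or 1/6 into 2/6, so escalation stops and the MTD is one level lower.

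**Working it through.** **Inputs.** Cycle length is 28 days (Section 5). Dabrafenib is given twice daily, trametinib and INCB039110 once daily (Table 5.1), so there are 4 doses a day and 4 x 28 = 112 per cycle. The missed-dose threshold is more than 20% (Section 5.3). The documents cite CTCAE version 4 but print no ALT grade limits, so I assume that Grade 3 starts at about 5x ULN. If it starts lower, the point covers Grade 3 rises from 5x ULN up.

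**The plan's own figure.** P(escalate) = (1-p)^3 + 3p(1-p)^5 gives 0.906, 0.709, 0.494, 0.309, 0.172 and 0.082 at p = 0.10 to 0.60. This reproduces the table in Section 13.1 (0.91, 0.71, 0.49, 0.31, 0.17, 0.08).

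**Where the scoring switches.** For a permanent stop before the dose on Day d, the days missed in Cycle 1 are 29 - d.

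| Stop day | Missed, per stopped drug | Over 20%? |
|---|---|---|
| 8 | 21/28 = 75% | yes |
| 15 | 14/28 = 50% | yes |
| 23 | 6/28 = 21.4% | yes |
| 24 | 5/28 = 17.9% | no |
| 26 | 3/28 = 10.7% | no |
| 28 | 1/28 = 3.6% | no |

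If the three drugs are pooled and INCB039110 continues, 3 of 4 daily doses are lost. Day 21 gives 24/112 = 21.4% and Day 22 gives 21/112 = 18.8%, so the switch comes at Day 22. If the stop day's dose has already been taken, each switch comes one day earlier. Doses missed earlier in the cycle move it later.

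**Can such an event be found that late?** The scheduled Cycle 1 panels after Day 1 are on Days 8 and 15 (Section 10: "Hematology and Blood Chemistry panels will be completed prior to Day 8 treatment", with a matching footnote for Day 15). There are three routes to a later finding:

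- Cycle 2 Day 1 is Day 29, and "Assessment for each visit can be done within 3 days of the projected visit date", so that panel may be drawn on Days 26-28.
- Table 6-14 lets a patient with ALT from 3x to below 5x ULN continue if weekly monitoring is possible. A rise found on Day 17 or 18 leads to a draw on Day 24 or 25.
- Table 6-2 requires liver tests in every pyrexia work-up. Pyrexia affected 71% of patients on the 150/2 doublet (Section 2.3.2.4).

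**What limits the group.** Recovery in under 7 days has to be documented. For criteria 2-6, Table 6-14 says "Repeat LFT and perform liver event follow up assessments within 24-72 hours", and monitoring is weekly after that. Recovery must therefore show at that repeat or at another draw before day 7. A Grade 3 rise not shown to clear in time is a DLT anyway.

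**Size.** The documents give no rate for related, Grade 3, brief ALT rises late in Cycle 1. The nearest figure is Grade 3-4 ALT over all treatment in the two doublet arms: 4% of 55 and 4% of 54, or about 2/55 + 2/54 = 4/109 = 3.7%. Spread evenly over Days 1-28 (an assumption), Days 24-28 hold 3.7% x 5/28 = 0.66 percentage points.

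- With other DLTs at 0.20: P(escalate) is 0.709 without these events and 0.694 with them, a difference of 0.014.
- With other DLTs at 0.30: 0.494 and 0.481, a difference of 0.013.
- Pooled switch (Days 22-28, 3.7% x 7/28 = 0.92 points) at 0.20: 0.709 and 0.689, a difference of 0.020.

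These overstate the effect, because the 3.7% includes Grade 4, slow-resolving and post-Cycle 1 events.

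**The case against.** **Denominator.** Section 5.3 does not say that the 20% is of Cycle 1 doses. A stop on Day 26 causes far more than 20% of later doses to be missed, so one could call it a DLT already. Section 13.1 weighs against this by judging tolerability on Cycle 1 only. It makes the Cycle 1 count the better reading, and it shows that a clarifying sentence is needed.

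**Design choice.** A cautious stopping rule for the individual need not define a DLT, and exempting brief laboratory rises is a legitimate decision. A late stop would also be seen by the data and safety monitoring committee, by the review before expansion, and in the expansion cohort of up to 20. This limits the harm but does not rescore the patient. Nor does the choice explain why the same event counts on Day 15 and not on Day 26.

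**Stronger readings that the documents do not support.**

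- A reader might infer that scoring is also open for stops through Day 23, because the exemption is worded categorically. But the missed-dose criterion is a separate, ungraded item, and the exemptions qualify the sentence on Grade 3 toxicity. Those stops are DLTs, and stating so is only a clarification.
- A reader might put the effect on escalation as high as 0.08 (0.709 to 0.629 when the whole 3.7% is added to 0.20). Only the late-cycle part changes its score.
- A reader might want every Table 6-14 stop to be a DLT. Criteria 1, 2 and 6 start at ALT 3x ULN, below Grade 3 on the assumption above and outside this gap. Criterion 6 turns on symptoms such as fatigue, nausea, fever and rash, which were common on the 150/2 doublet (53%, 44%, 71% and 45%), and the cost cannot be quantified from the documents. Criterion 5, where ALT "cannot be monitored weekly for 4 weeks", is partly logistical.

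**Conclusion.** The point holds, and it is minor. As written, a related Grade 3 ALT rise first acted on from about Day 24 that clears in under 7 days, with no other DLT, is a non-DLT although it ends two of the three drugs. The difference from an earlier event comes only from cutting the missed-dose count off at Day 28.

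If Grade 3 starts at about 5x ULN and Table 6-14 is followed, the ALT exemption changes the score only in those last few days of Cycle 1. Before then, the mandated stop makes the event a DLT through missed doses.

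The conclusion rests on three assumptions: the Grade 3 limit, a Cycle 1 denominator for missed doses, and a per-drug count (pooling moves the switch to about Day 22). The effect on the probability of escalating is about 0.01 at a DLT rate of 0.20 under an even spread that overstates it. The INCB039110 triplet's own rate is unknown.

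**What to change.** Add to Section 5.3:

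> The Grade 3 exemptions do not apply to a treatment-related Grade 3 ALT rise in Days 1-28 that requires permanent discontinuation of dabrafenib and trametinib under Table 6-14; such an event is a DLT, and the missed-dose criterion applies regardless of the exemptions.

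Leave ALT events below Grade 3 (criteria 1, 2 and 6) out of the DLT definition.

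This needs no new test, visit or patient. It also lets the event be scored when treatment is stopped. Otherwise, for a rise on Days 26-28, the 7-day recovery may still be pending when the escalation decision is due at the end of Cycle 1. The cost is that the ALT exemption keeps little or no effect, and that a few late, brief rises become DLTs, with the small fall in the probability of escalating shown above.
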